6.3 Risks to Study Participants

Blindness from infectious corneal ulcers is a worldwide public health problem. If our hypothesis is correct, and corneal crosslinking provides an additive benefit to topical antimicrobials in the treatment of corneal infections, there could potentially be a profound societal benefit. The process of corneal cross-linking is painless. Adverse events associated with corneal cross-linking appear to be exceedingly rare. A recent publication of 3-year follow-up of 100 keratoconus eyes, found two adverse events: one instance of corneal infection and one case of corneal edema, which resolved within one week.¹³ In a series of 16 patients with bacterial ulcers and presenting average visual acuity of approximately 20/100 (including one patient with 20/20 vision) no complications or side effects of treatment were observed.¹¹ Additionally, a meta-analysis of the literature concerning cross-linking for infectious keratitis concluded that the available evidence supports the use of cross-linking for the treatment of infectious keratitis.⁵ All procedures will be performed by ophthalmologists board certified in the study country who are well versed in all planned treatment procedures.

We anticipate minimal risk for study patients. This fact, coupled with the potential benefit the data provided by the study could provide in terms of guiding future therapies for corneal infections, makes the minimal risks posed to the patient entirely reasonable.

There may be some discomfort during follow-up testing (BSCVA, IOP, slit lamp, Pachymeter, Topography, and photo imaging of the eye), but this will be kept to a minimum. The participant will be asked to tell the doctor if any of this testing feels painful. There may be a medication reaction such as eye irritation, swelling, pain, redness, or discharge. If this occurs the risks of stopping the medication must be weighed against the severity of infection and other treatment options.

6.4 Privacy, Confidentiality and Data Security

All data will be stored and transferred using a secure server with de-identified information.

We will take steps to keep the participant's personal information confidential. Health information will be kept secure and separate from information which identifies participants. Upon enrollment, participants will be assigned a code that will be used instead of their name, medical record number or other personally identifying information. Electronic files for data analysis will contain only the participant code. The code will be stored at Aravind on a secure server and will only be accessed by study personnel – the PI, study coordinator, or other member of the study team). Access to study-related patient information will be limited only to members of the study team.

Only a small number of researchers related to this study will have direct access to the participant's medical information. Paper files will be stored in locked filing cabinets in restricted access offices at Aravind. Access to data/specimens is restricted to study personnel.

Information may be released to others outside of Aravind who are involved in coordinating or overseeing research, but information which identifies the participant will be kept secure. To ensure the success of this study, Aravind has partnered with University of California, San Francisco (UCSF)'s F.I. Proctor Foundation, which is a center that specializes in ophthalmology research. The coordinating center at UCSF will have access to de-identified information using a code number. UCSF's role is to support Aravind on the data analysis portion of this study and assisting with the development of consent and study-related materials. UCSF has obtained IRB approval to take part in this study (IRB number: #14-14918).

6.5 Exclusion of Vulnerable Populations

The following populations will not be enrolled in this study: children (18 years and under), pregnant women, decisionally impaired adults, and prisoners.

6.6 Compensation to Participants

There is no additional cost or compensation for the study participant.

7. DATA COLLECTION AND MANAGEMENT

7.1 Data Collection and Entry

All data will be collected using hardcopy patient forms at Aravind during baseline and follow-up visits. Deidentified data will be uploaded to a Box account in order to share the data with the UCSF study coordinator. Deidentified data will be input into a database using double data entry at UCSF.

7.2 Data Consistency, Validity, and Monitoring

Data monitoring reports will be prepared using STATA and Excel. If the forms are not filled out completely, the UCSF study coordinator will contact the person responsible for completing the form to provide the missing data, or clarify any inconsistent data. The Aravind study coordinator is the only person who is authorized to add missing data or make any changes to the study forms. All changes should be made with a red ink pen, and then signed and dated.

7.3 Data Storage and Security

De-identified data will then be input into a database using double data entry at UCSF. Data will be stored at UCSF for about 10 years.

8. STATISTICAL ANALYSIS PLAN

Please see the **Statistical Analysis Plan (SAP)** for details on the statistical analysis.

#### 1. Background

Cross-Linking Assisted Infection Reduction (CLAIR) I for bacterial ulcers, CLAIR II for fungal ulcers are two randomized, masked, clinical trials. The purpose of these studies is to determine differences in microbiological cure for repeat cultures between different medical antimicrobial treatments alone versus antimicrobial treatment plus collagen cross-linking. There will be 1:1 randomization to each of these treatment groups:

#### CLAIR I. Bacterial Ulcers:

- 1) Topical 0.5% Moxifloxacin alone
- 2) Topical 0.5% Moxifloxacin plus cross-linking

### CLAIR II. Fungal Ulcers:

- 1) Topical 5% natamycin alone
- 2) Topical 5% natamycin plus cross-linking
- 3) Topical 0.15% amphotericin alone
- 4) Topical 0.15% amphotericin plus cross-linking

### 2. Statistical Considerations, Sample Size

We will perform separate analyses for each specific aim for (I) the bacterial ulcers, (II) the fungal ulcers. Enrollment criteria require all study participants to have bacteria on smear from corneal scrapping. Previous studies have shown that 88% of bacterial cultures are positive when initial gram stain is positive. This is consistent with the experience of the microbiology lab at our own institution. We feel that this is a conservative estimate based on prior studies in a similar south Indian setting that have found approximately 90-95% of corneal scrapings with a positive Gram/KOH stain are also culture positive.

There is little current data to inform us about the effect of repeat scrapping on the culture status. In the Mycotic Ulcer Treatment Trial II, approximately 55% of fungal ulcers were culture positive 6 days after enrolling in the trial and receiving treatment. This is an approximately 7.5% reduction is culture positivity on average per day. If we consider initial scrapping to have a similar effect as one day of treatment, we can estimate that there would be an approximately 8% reduction in culture positivity due to repeat scraping in our trial.

#### SPECIFIC AIM 1 analysis:

CLAIR I Bacterial Trial: McNemar's two-sample paired-proportions test will be used to compare pre- and post- cross-linking cultures on smear-positive bacterial corneal ulcers. In order to detect a 30% difference in repeat culture status (80% in the control group vs. 50% in the crosslinking group), we would need to enroll 78 study participants, assuming a significance level of 0.05 and no loss to follow-up (since the primary outcome occurs the same visit as enrollment).

CLAIR II Fungal Trial: Given the 4 arms of the trial, we have estimated a sample size based on a significance level of 0.0125. In order to detect a 30% difference (80% in control versus 50% in the crosslinking group), we would need to enroll 110 study participants. This assumes no loss to follow-up, since the primary outcome occurs at the same visit as enrollment. In reality, we should have more statistical power since we will also take into account the results of the baseline culture, which we expect to be highly correlated with the follow-up culture.

1 | Page Version 1.4

SPECIFIC AIM 2 analysis: 3-month best spectacle-corrected visual acuity (BSCVA) will be examined in a multiple linear regression model with terms for treatment (dichotomous variable for bacterial and 4-level categorical variable for fungal ulcers) and baseline BSCVA. Similar to above, for the fungal ulcers we will first test for an overall difference between the 4 groups, then pairwise comparisons as indicated, using a Bonferroni correction. 3 and 12-month best spectacle-corrected visual acuity (BSCVA) will be examined in a repeated measures multiple linear regression model with terms for treatment (dichotomous variable for bacterial ulcers and 4-level categorical variable for fungal ulcers) and baseline BSCVA. Similar to above, for the fungal ulcers we will first test for an overall 12-month BSCVA difference between the 4 groups, then pairwise comparisons as indicated, using a Bonferroni correction.

For study participants who experience perforation or undergo therapeutic penetrating keratoplasty (TPK) this will be noted and a BSCVA will be performed prior to performing further surgery. This last observation will be carried forward (LOCF) as the 3-month BSCVA. An enhanced analysis using standard longitudinal modeling methods will be used to handle data from study participants who are lost to follow up. Additional secondary analyses will include:

- Scar size as measured on clinical exam and photographs
- Corneal topography
- Corneal Thickness and scar size as measured by OCT
- IND-VFQ will be compared between the two groups controlling for baseline VFQ
- Analyses of perforations or other adverse events
- A cost effectiveness analysis will be performed.

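### The only primary test named for CLAIR I is a before-and-after McNemar test that leaves out the control arm, so it cannot show that cross-linking adds anything

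*SAP*

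**What the plan says.** SAP section 2, Specific Aim 1, gives one analysis for the bacterial trial: "McNemar's two-sample paired-proportions test will be used to compare pre- and post- cross-linking cultures on smear-positive bacterial corneal ulcers". The next sentence sizes the trial on a different contrast, "80% in the control group vs. 50% in the crosslinking group", and concludes that "we would need to enroll 78 study participants, assuming a significance level of 0.05". Power and sidedness are not stated.

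Everything else in the documents describes a comparison between arms:

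- SAP section 1 gives the purpose as comparing "antimicrobial treatments alone versus antimicrobial treatment plus collagen cross-linking", with 1:1 allocation.
- Protocol 1.1 hypothesises more negative cultures in the CXL group than in the comparator.
- Protocol 3.3 uses block randomisation, which creates no matched pairs across arms, and commits to intention to treat.
- Protocol 3.4 has both CLAIR I arms re-scraped at 4 hours, with moxifloxacin starting only afterwards.

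On what happens without CXL, SAP section 2 puts baseline culture positivity at 88% when the Gram stain is positive and adds that "we can estimate that there would be an approximately 8% reduction in culture positivity due to repeat scraping in our trial". Protocol section 8 leaves all analysis to the SAP, so no CLAIR I primary test is specified elsewhere.

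**The concern.** McNemar's test asks whether a proportion changes between two measurements on the same eye. Eyes in the two arms are different, independent eyes, so the test cannot compare CXL with control. A control eye has no culture after cross-linking and, read literally, does not enter the analysis.

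In CLAIR I the antibiotic starts after the 4-hour scraping. The main reasons other than CXL for a culture to turn negative are therefore the earlier scraping and ordinary culture variability. Both act equally in the control arm, and only that arm can separate them from a CXL effect. The named test credits all of the clearance to CXL.

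Two things are at stake. A significant result would not support the conclusion that CXL adds to antimicrobial treatment. And for that question the type I error is not held at 5%.

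**Working it through.** **1. Reproducing the 78.** From the SAP: 80% and 50% positive, alpha 0.05, 1:1 allocation, no loss to follow-up. Assumed: two-sided test, 80% power. The pooled formula for two independent proportions, with mean proportion 0.65, is

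n per arm = [1.960·√(2·0.65·0.35) + 0.842·√(0.80·0.20 + 0.50·0.50)]² / 0.30²
= (1.322 + 0.539)² / 0.09 = 38.48, rounded up to 39 per arm, **78 in total**.

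This matches exactly. Other choices do not: unpooled variance gives 72, a continuity correction 90, a one-sided test 62, and 90% power 104.

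**2. Sizing for the test actually named.** McNemar's test depends on the two discordant proportions: p10 (positive to negative) and p01 (negative to positive).

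pairs = [1.960·√(p10+p01) + 0.842·√(p10+p01−d²)]² / d², with d = p10−p01 = 0.30

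- No within-eye correlation (p10 = 0.40, p01 = 0.10): (1.386 + 0.539)² / 0.09 = 41.2, so 42 pairs.
- No reverse changes (p10 = 0.30, p01 = 0): (1.074 + 0.386)² / 0.09 = 23.7, so 24 pairs.

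Starting from the SAP's 88% baseline instead of 80%, the range is 19 to 25 pairs. None of these gives 78.

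**3. False-positive rate if CXL has no effect.** Take the SAP's own fall, 88% to 80%. The documents give only these margins, so the split between the two kinds of change is an assumption. The table shows the probability, by exact enumeration, that McNemar's test rejects at nominal 0.05 in the 39 CXL eyes.

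| Positive→negative / negative→positive (points) | Exact | Uncorrected chi-square |
|---|---|---|
| 8 / 0 | 8.8% | 38% |
| 10 / 2 | 10.5% | 29% |
| 12 / 4 | 10.8% | 22% |
| 16 / 8 | 9.7% | 15% |

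The first row can be followed by hand. With no reverse changes, the exact test rejects once 6 eyes have cleared (2 × 0.5⁶ = 0.031), and the chance of at least 6 among 39 at 8% is 0.088. The uncorrected test rejects at 4, with chance 0.381.

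**4. Two further cases.**

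- If the test were run on all 78 eyes, pooling the arms (a different reading, which the SAP wording hardly supports), the exact test would reject 60%, 42%, 32% and 23% of the time for the same four splits.
- If scraping cleared 15 points (an assumption with no source in the documents), the exact test in 39 eyes would reject 54% of the time with no reverse changes, 41% for an 18/3 split and 35% for 20/5.

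**5. A between-arm test of the same size.** With 39 per arm, the Pearson test has a type I error of 5.1% when both arms are at 80%. Its power for 80% against 50% is 81.3% by enumeration and 80.5% by normal approximation.

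**The case against.** The best defence is that a comparison of arms was plainly intended. The sizing sentence, the trial purpose, the Aim 1 hypothesis and the intention-to-treat commitment all say so, which would make the McNemar sentence a misnaming. The evidence of intent is real, and it is why 78 needs no change. But intent does not supply a test. An analyst following the SAP would run the wrong analysis or choose a replacement after the data exist. Calling the test two-sample does not help, because the SAP defines the pairs as cultures before and after cross-linking. The remark about using the baseline culture is in the CLAIR II paragraph and names no model.

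The objections to the size of the inflation partly stand. The discordance splits are assumed, and wider splits lower the uncorrected rates. The SAP does not say which form of McNemar's test it means, and in its exact form the inflation in 39 eyes is moderate. The 8-point figure is itself soft: it is extrapolated from fungal ulcers under treatment, and the SAP admits that data are scarce. The masked sample-size review in SAP section 3 responds to that uncertainty but does not repair the test. All of this affects how large the error is, not whether it exists.

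The upper end of the McNemar sizing, 42 pairs, is close to 39. That looks like coincidence, since the SAP labels the 80% as the control group and 78 as the number to enrol.

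**Conclusion.** The concern holds. The CLAIR I primary analysis as written does not test the randomised comparison, and no other text supplies a test that does. Under the SAP's own 88% to 80% fall and no CXL effect, the false-positive rate in 39 CXL eyes is about 9–11% (exact) or 15–38% (uncorrected), against a nominal 5%. It rises quickly if scraping clears more than 8 points. These rates rest on the assumed splits, but every scenario examined exceeds 5%. The main objection does not depend on them: a significant change from before to after CXL would not show that CXL adds to antimicrobial treatment.

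The number 78 is sound for a between-arm comparison, provided the sponsor confirms a two-sided 5% level and 80% power. This must be corrected before analysis because it decides whether the primary conclusion is valid.

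**What to change.** Replace the McNemar sentence with one named between-arm test: culture positivity at the scheduled 4-hour repeat scraping, CXL against control, by intention to treat, accounting for the baseline culture result. A Mantel-Haenszel risk difference stratified by baseline culture fits the sizing, which is stated as a difference in percentages. Logistic regression with terms for arm and baseline culture is an acceptable alternative but estimates an odds ratio, so the SAP should name one of the two as primary. About 9 of the 78 eyes (0.12 × 78 = 9.4) would be culture-negative at baseline, so the SAP should also say what is done if that stratum is too sparse.

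Keep 78 and state its basis: two independent proportions, 80% against 50%, 39 per arm, with the sidedness and power the sponsor confirms. Any McNemar result should be descriptive, within each arm separately.

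The cost is SAP wording only. No extra patients, visits or data are needed, since both arms are already cultured at baseline and at 4 hours.

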- Change in IND-VFQ from baseline to 3 months.

1.3 Study Design:

Cross-Linking Assisted Infection Reduction (CLAIR) I for bacterial ulcers and CLAIR II for fungal ulcers is a series of randomized, masked, clinical trials. The purpose of these studies is to determine differences in microbiological cure for 1-day repeat cultures between different medical antimicrobial treatments alone versus antimicrobial treatment plus collagen cross-linking. There will be 1:1 randomization to each of these treatment groups:

CLAIR I. Bacterial Ulcers:

- 1) Topical 0.5% Moxifloxacin alone
- 2) Topical 0.5% Moxifloxacin plus cross-linking

CLAIR II. Fungal Ulcers:

- 1) Topical 5% natamycin alone
- 2) Topical 5% natamycin plus cross-linking
- 3) Topical 0.15% amphotericin alone
- 4) Topical 0.15% amphotericin plus cross-linking

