3.4 Study visits

3.3.1 Baseline Visit. During this visit, eligible patients will be enrolled in the study and will give consent. The baseline patient form will be completed and baseline topography will be obtained.

CLAIR I. Bacterial Ulcers:

Study participants will be randomized to one of two possible treatment arms: 1) topical 0.5% moxifloxacin alone 2) topical 0.5% moxifloxacin plus CXL. Those randomized to CXL will undergo the procedure in the operating theatre within 4 hours. Both arms will undergo repeat scraping at 4 hours post enrollment. Thereafter, all study participants will start 0.5% moxifloxacin every hour. All patients will be admitted to the inpatient setting until the 3^{rd} day.

CLAIR II. Fungal Ulcers:

They will be randomized to one of four possible treatment arms 1) topical 5% natamycin alone, 2) topical 5% natamycin plus CXL, 3) topical 0.15% amphotericin alone or 4) topical 0.15% amphotericin plus CXL. All study participants will begin medical therapy immediately (either natamycin or amphotericin) every hour and those randomized to CXL will undergo the procedure in the operating theatre within 24 hours. All study participants will undergo repeat scrapping at 24 hours from enrollment. All patients will be admitted to the inpatient setting until the 3^{rd} day.

- *3.3.2 Procedure visit.* All study participants randomized to CXL will have the procedure in the operating theater. This will occur within 4 hours for bacterial ulcers and within 24 hours of the baseline visit for fungal ulcers. Once a study participant has been randomized to treatment, he will have the treatment even if there is a delay in the operating theatre that results in delayed treatment, however re-scraping will occur at 4 hours for bacterial ulcers and 24 hours for fungal ulcers even if they have not yet had cross-linking. If the cross-linking occurs after repeat scrapping, a third smear and culture should be performed.
- *3.3.3 Day 3 visit.* During this visit, study participants will have BSCVA recorded, IND-VFQ, slit lamp examination and undergo repeat scraping and culture of the corneal ulcer. Thereafter, all additional treatments including but not limited to topical antimicrobials, or oral antimicrobials, will be at the clinician's discretion. At this point patients may be discharged from the inpatient setting.
- 3.3.4 *3 week visit.* During this visit study participants will have BSCVA recorded, slit lamp examination, and they will have digital photography.

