- 3.3.5 Final Visit. At the 3- Month visit study participants will have their BSCVA and slit lamp examination recorded, in addition to repeat topography and be administered the IND-VFQ.

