3.5 Study Schedule

	Visit 1	Visit 2	Visit 3	Visit 4	Visit 5
	Baseline Exam	Procedure & Repeat Culture	3-Day Repeat Culture	3 week Follow-up	Month 3 Final
Forms					
Consent and Authorization form	X				
Baseline form	X				
NEI-VFQ			X		X
Follow-up form			X	X	X
Final form					X
Procedures					
Cross-linking		X			
Tests					
IOP	X		X	X	X
Pachymetry U/S	X		X	X	X
Pentacam Topography	X				X
Slit Lamp Photography*	X			X	X
BSCVA/ETDRS/MRx		X		X	X
Total visit time	2 hours	2 hours	2 hours	1 hour	1 hour
	* Slit lamp photography also taken upon an adverse even				an adverse event

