4. PROCEDURES

4.1 Masking

Due to the nature of the intervention, the study participant, surgeon and technician performing cross-linking will not be masked, however, the physician performing repeat scraping as well as the microbiologist will be masked to treatment arm. The refractionist performing the BSCVA will also be masked. UCSF study personnel will not be given any identifying information.

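### The IND-VFQ analysis needs a baseline score, but the questionnaire is scheduled only at Day 3 and Month 3, after randomisation and planned cross-linking

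*SAP*

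**What the plan says.** **Outcome and analysis.** Protocol 1.2 lists as a secondary outcome "Change in IND-VFQ from baseline to 3 months". The list of additional secondary analyses in SAP section 2 says "IND-VFQ will be compared between the two groups controlling for baseline VFQ".

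**Visit descriptions (Protocol 3.4, items numbered 3.3.1 to 3.3.5).** For the baseline visit, after enrolment and consent: "The baseline patient form will be completed and baseline topography will be obtained". No visual-function questionnaire is named there. It first appears at Day 3: "During this visit, study participants will have BSCVA recorded, IND-VFQ, slit lamp examination". It appears once more at the final visit: "in addition to repeat topography and be administered the IND-VFQ".

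**Schedule (Protocol 3.5).** The questionnaire has its own row, labelled NEI-VFQ instead of IND-VFQ. It is marked at Visit 3 (3-day) and Visit 5 (Month 3) and is blank at Visit 1. The baseline form is a separate row, marked at Visit 1.

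**Masking (Protocol 4.1).** "the study participant, surgeon and technician performing cross-linking will not be masked".

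**Visual acuity, a lesser point.** The SAP also adjusts BSCVA for its baseline value. The schedule row "BSCVA/ETDRS/MRx" is first marked at Visit 2, the visit text first mentions BSCVA at Day 3, and neither lists it at Visit 1.

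**The concern.** A baseline covariate, or the starting value of a change score, should be fixed before the treatments can act on it. The only early IND-VFQ score in this plan comes about three days after randomisation. By then CXL is due to have been done (within 4 hours in CLAIR I, 24 hours in CLAIR II) and hourly drops have been running. In CLAIR II the arms also differ by drug. Participants know whether they had CXL and complete a questionnaire about their own visual function, so knowledge of the arm can affect the score as well as any real early effect.

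An analyst following the SAP literally has no baseline to use. The obvious improvisation is the Day-3 score, which would remove part of the treatment effect or add to it. Neither document names Day 3, or any other score, as the baseline.

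**Working it through.** The plan gives no figure for this outcome, so there is none to reproduce. The check is a comparison of passages, followed by the consequence.

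**1. Where the questionnaire is given**

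| Source | Visit 1 | Day 3 | Month 3 |
|---|---|---|---|
| Protocol 1.2 (outcome) | needed | – | needed |
| SAP section 2 (analysis) | needed | – | needed |
| Protocol 3.4 (visit text) | not named | named | named |
| Protocol 3.5 (schedule) | blank | X | X |

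The visit text and the schedule agree with each other and conflict with the outcome and the analysis. A table cell displaced in the PDF text would not explain that agreement.

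**2. What is estimated if Day 3 stands in for baseline**

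Let T be the true arm difference at Month 3, D the true arm difference at Day 3, and b the within-arm slope of the Month-3 score on the Day-3 score.

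- Change score: T − D
- Adjusted comparison: T − b × D
- Month-3 comparison ignoring Day 3: T

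With f = D/T, the first two recover 1 − f and 1 − b × f of T. Values of f and b are assumed, because the documents give none:

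| f | Change score | Adjusted, b = 0.3 | b = 0.5 | b = 0.7 |
|---|---|---|---|---|
| +0.5 | 50% | 85% | 75% | 65% |
| −0.5 | 150% | 115% | 125% | 135% |

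The bias vanishes if D = 0 (or, for the adjusted comparison, if b = 0).

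**3. Precision lost if there is no baseline IND-VFQ**

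95% CI half-width in SD units = t(0.975) × √(2/n per group) × √(1 − r²), where r is the correlation between a true baseline and Month 3 (assumed). The n per group comes from the SAP totals: 78/2 = 39 in CLAIR I, and 110/2 = 55 in CLAIR II for CXL against no CXL. No loss to follow-up is assumed.

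| Trial | No baseline | r = 0.3 | r = 0.5 | r = 0.7 |
|---|---|---|---|---|
| CLAIR I, 39 per group | 0.45 | 0.43 | 0.39 | 0.32 |
| CLAIR II, 55 per group | 0.38 | 0.36 | 0.33 | 0.27 |

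The variance without a baseline, relative to that with one, is 1/(1 − r²) = 1.10, 1.33 or 1.96.

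**The case against.** The strongest reply is that this is a clerical slip. A baseline is clearly intended in two places, and the documents have other slips of the kind: two names for the questionnaire, 6- and 12-month image labels in a 3-month study, and a 3-week visit called 1-month elsewhere. The contents of the baseline form are not given, so it could hold an IND-VFQ. The baseline visit text is also not exhaustive, since it omits IOP, pachymetry and photography that the schedule marks at Visit 1.

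Part of this stands. The silence of the visit text is weak evidence by itself, and a baseline score missing only from the paperwork cannot be excluded. But the schedule does list Visit 1 procedures, gives the questionnaire its own row apart from the baseline form, and leaves that cell blank. If a score is collected, the passages still need correcting.

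The numbers are also open to challenge. The values of f, b and r are illustrative. The SAP's no-loss assumption covers only the primary outcome, so losses by Month 3 would widen the intervals. The SAP line speaks of two groups, but CLAIR II has four arms; a pairwise comparison at 110/4 = 27.5 per arm has a half-width of about 0.54 SD, not 0.38. A pre-treatment BSCVA could recover some of the lost precision, so the variance ratios are upper figures for each r. All of this is fair, and none of it supplies the missing baseline.

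The BSCVA point is weaker. The Visit 2 mark may be displaced in the PDF text, a pre-CXL value at Visit 2 would precede all study treatment in CLAIR I, and "The refractionist performing the BSCVA will also be masked". It is a matter for reconciliation, not a shown bias.

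**Conclusion.** The concern holds. The stated IND-VFQ outcome and analysis cannot be carried out from the scheduled assessments without using a post-randomisation score, from unmasked participants, as baseline. The size and direction of the resulting bias cannot be stated from the documents: it depends on the Day-3 arm difference, can hide or inflate an effect, and is zero only in the cases given above. Leaving Day 3 out avoids the bias at a cost in precision that depends on the assumed correlation. The damage is confined to a secondary outcome; the primary culture outcome and the sample size are not affected. It should still be corrected, because a pre-treatment score that was never taken cannot be recovered later.

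**What to change.** **Protocol.** Administer the questionnaire at Visit 1, after consent and before randomisation. Move the Day-3 administration there, or keep Day 3 as follow-up only. Show this in item 3.3.1 and in the 3.5 table, and use one instrument name throughout.

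**SAP.** State that baseline IND-VFQ is the Visit 1 score, that the Day-3 score may not be used as baseline, and which groups are compared in CLAIR II. For participants already enrolled without a pre-treatment score, compare Month-3 scores without subtracting or adjusting for Day 3, and rename the outcome accordingly.

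**BSCVA.** Reconcile Protocol 3.4 with 3.5, and state in the SAP that baseline BSCVA is a value taken before study treatment. In CLAIR I this may be a pre-CXL Visit 2 value.

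**Cost.** A protocol amendment and one questionnaire, offset if Day 3 is moved. Timing needs care in CLAIR I, where the re-scrape is at 4 hours post enrolment and moxifloxacin follows it. Visits 1 and 2 are listed at 2 hours each, and CXL takes 30 + 30 = 60 minutes. If the clock starts when Visit 1 starts, slack is 4 − 2 − 2 = 0 hours; if when Visit 1 ends, 4 − 2 = 2 hours. The zero is a worst case, because the re-scrape falls inside Visit 2. The documents do not say when the clock starts, and Protocol 3.3 gives 3 hours for the procedure where 3.4 gives 4; these passages must be reconciled first.

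A questionnaire given before the clock starts would delay the first study drops by its own length. That length is not given; an assumed 10 to 20 minutes is 10/240 = 4% to 20/240 = 8% of the 4 hours. In CLAIR II drops begin immediately after enrolment, so the same delay would apply to their start. Whether it is acceptable is for the investigators to settle.
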